- When up to 3 additional patients are added to a given dose level, if 0-1 of 6 patients has a DLT then the dose will be increased to the next dose level.
- Additional dose levels may be explored per investigator discretion to define the safety profile of the treatment.

The recommended Phase II dose (RP2D) will be the highest cohort level in which one or fewer subjects of 6 develops a first cycle DLT.

The Data and Safety Monitoring Committee as described below will regularly review all serious adverse events and any local adverse events, which are unanticipated problems. The study will utilize the Common Terminology Criteria for Adverse Events (CTCAE) version 4.03 for grading of all adverse events related to treatment.

Table 6.2: Dose-limiting toxicity: phase Ib component

The following will be considered a DLT if they occur within the first cycle of therapy with LEE011 and are determined to be possibly, probably or definitely related to LEE011

Grade 4 neutropenia lasting more than 7 consecutive days
Grade 3 or 4 febrile neutropenia
≥ Grade 3 vomiting ≥ 48 hours despite optimal anti-emetic therapy
≥ Grade 3 diarrhea ≥ 48 hours despite optimal anti-diarrhea therapy
Clinical signs of cardiac disease, such as unstable angina or myocardial infarction, or Troponin ≥ grade 3
Grade 4 serum alkaline phosphatase > 7 days
≥ Grade 3 serum creatinine
≥ Grade 3 adverse event for any non-hematologic toxicity unless otherwise specified as below (excluding alopecia, fatigue < 5 days, laboratory abnormalities that are responsive to oral supplementation or deemed by the investigator to be clinically insignificant).

THROMBOCYTOPENIA	
Toxicity/Grade	Dose Limiting Toxicity and Management Recommendations
Grade 3 ($\geq 25 \times 10^9/L$ - $<50 \times 10^9/L$) without clinically significant bleeding	Dose interruption until recovery to grade ≤ 2 . Re-initiate LEE011 at the same dose level. • If toxicity recurs at grade 3: dose limiting toxicity
Grade 3 ($\geq 25 \times 10^9/L$ - $<50 \times 10^9/L$) with clinically significant bleeding	Dose limiting toxicity
Grade 4 ($<25 \times 10^9/L$)	Dose limiting toxicity

HEPATOTOXICITY (BILIRUBIN, ALT, AST)	
TOTAL BILIRUBIN without ALT/AST increase above baseline value	
Toxicity/Grade	Dose Limiting Toxicity and Management Recommendations
Same grade as baseline or increase from baseline grade 0 to grade 1	Maintain dose level with LFTs monitored every other-week

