Grade 3 ANC $< 1.0 \times 10^9/L$ with [a single temperature of $> 38.3^\circ C$ ($101^\circ F$) or a sustained temperature of $\geq 38^\circ C$ ($100.4^\circ F$) for more than one hour]	Dose interruption until improvement of ANC $\geq 1.0 \times 10^9/L$ and no fever. Restart at the next lower dose level. 
 If febrile neutropenia recurs, discontinue LEE011.
Grade 4 Life-threatening consequences; urgent intervention indicated	Discontinue LEE011.
Anemia (Hemoglobin)	
Grade 1 (≥ 10.0 g/dL)	No dose adjustment required.
Grade 2 ($\geq 8.0 - < 10.0$ g/dL)	No dose adjustment required.
Grade 3 (< 8.0 g/dL)	Dose interruption until recovery to grade ≤ 2 . Re-initiate LEE011 at the same dose.

Grade 4 Life-threatening consequences; urgent intervention indicated	Discontinue LEE011.
---	---------------------

**Table 6-5 LEE011 Dose Adjustment and Management Recommendations for
HEPATIC ADVERSE REACTIONS**

HEPATOTOXICITY (BILIRUBIN, ALT, AST)	
TOTAL BILIRUBIN without ALT/AST increase above baseline value	
Grade	Dose Adjustment and Management Recommendations
Same grade as baseline or increase from baseline grade 0 to grade 1	Maintain dose level with LFTs monitored every other-week
Increase from baseline grade 0 or 1 to grade 2 (1.5-3.0 x ULN) or from baseline grade 2 to grade 3 (>3.0 -10 x ULN)	Dose interruption of LEE011 If resolved to \leq grade 1 in \leq 21 days, then maintain dose level If resolved to \leq grade 1 in $>$ 21 days or toxicity recurs, discontinue LEE011

Increase from baseline grade 0 or 1 to grade 3 (>3.0-10 xULN)	Discontinue LEE011
Grade 4 (> 10.0 x ULN)	Discontinue LEE011

Confounding factors and/or alternative causes for increase of total bilirubin should be excluded before dose interruption/reduction. They include but are not limited to: evidence of obstruction, such as elevated ALP and GGT typical of gall bladder or bile duct disease, hyperbilirubinemia due to the indirect component only (i.e. direct bilirubin component ≤ 1 x ULN) due to hemolysis or Gilbert Syndrome, pharmacologic treatment, viral hepatitis, alcoholic or autoimmune hepatitis, other hepatotoxic drugs.
 
For patients with Gilbert Syndrome, these dose modifications apply to changes in direct bilirubin only. Bilirubin will be fractionated if elevated.
	
HEPATOTOXICITY (BILIRUBIN, ALT, AST)	
AST or ALT without bilirubin elevation > 2 x ULN	
AST or ALT Toxicity/Grade	Dose Adjustment and Management Recommendations

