6.12.4 CHEMOEMBOLIZATION PROCEDURAL PREPARATION

- a) The patient is prepped and draped in a sterile fashion.
- b) Carefully evaluate the vascular network associated with the lesion with high resolution imaging prior to beginning the embolization procedure.

- c) DC beads are available in a range of sizes, but only 100 to 500 um particles should be utilized. Care should also be taken to choose the appropriate size of DC bead that bases matches the vascular target or vessel size.
- d) Choose a delivery catheter based on the size of the target vessel. DC bead can tolerate temporary compression of 20% to 30% in order to facilitate passage through the delivery catheter.
- e) Introduce the delivery catheter into the target vessel according to standard techniques. Position the catheter tip as close as possible to the treatment site to avoid inadvertent occlusion of normal vessels.
- f) DC are not radio-opaque. It is recommended to monitor the embolization under fluoroscopic visualization by adding the desired amount of contrast medium to the suspension fluid.
 - a. Take care to ensure proper suspension of the DC bead in the contrast medium to enhance distribution during injection.
 - b. Draw the DC bead into a syringe needle of a size greater than or equal to 19 gauge.
 - c. At a rate no faster than 1ml/minute, slowly inject DC bead into the delivery catheter under fluoroscopic visualization while observing the contrast flow rate. Exercise conservative judgment in determining the embolization endpoint.
- g) Upon completion of the treatment, remove the catheter while maintaining gentle suction so as not to dislodge the DC bead still within the catheter lumen.
- h) Discard any unused DC bead loaded with doxorubicin.

6.12.5 **POST-CHEMOEMBOLIZATION PROCEDURE ORDERS AND CARE**

- a) Admit patients overnight for observation.
- b) Hydration with IV normal saline
- c) Patient controlled analgesia for pain control.

6.12.6 **POST-PROCEDURE CARE**

- a) Post-arteriography bedrest with monitoring of vital signs and pulses.
- b) Patient can be discharged as soon as they demonstrate adequate oral intake or liquids, no longer require parenteral narcotics or antiemetics.
- c) Fevers <103 degrees F are normal during the first week following treatment and do not require cultures.
- d) Following institutional guidelines, patients will be seen in the HCC multidisciplinary clinic 7-10 days following chemoembolization and will have the following evaluations completed:

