6.12.7 Subsequent Chemoembolizations

To proceed with subsequent chemoembolization, study subjects must meet the following criteria:

- \leq Grade 2 hematologic toxicity with the exception of:
 - serum creatinine $\leq 1.5 \text{ mg/dl}$;
 - serum bilirubin $\leq 3.0 \text{ mg/dl}$.

Repeat Chemoembolization (for either ipsilateral or contralateral disease) if indicated, should be performed at least 4 weeks apart. Up to 4 chemoembolizations can be performed in 6 months of the first chemoembolization. Additional chemoembolizations, if clinically indicated can occur after the first 6 months

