7.1 TABLE OF ASSESSMENTS

Treatment Days	Screening Phase ¹		Treatment Phase: Chemoembolization	Treatment Phase: LEE011						Post Treatment Follow-up			Survival Phase
	Day -28 – Day -1	Day -7 – Day -1	7-14 days Following chemoembolization	Cycle 1		Cycle 2		C3	C4+	End of Treatment or Early Withdrawal (Within 15 Days of Last LEE011 Dose)	Safety Follow-Up (Within 30 Days of Last LEE011 Dose)	Efficacy Follow-Up	Survival Follow-Up Every 12 weeks
Visit Assessments				Day 1 ^{2,13}	Day 15	Day 1	Day 15	Day 1	Day 1				
Informed Consent	X												
Demographics	X												
Eligibility Checklist - Inclusion / Exclusion	X												
Med History	X												
Dx and Extent of Cancer (Staging)	X												
Physical Exam		X	X	X	X	X	X	X	X	X	X		
ECOG Status		X	X	X	X	X	X	X	X	X	X		
Height	X												
Weight		X		X	X	X	X	X	X	X	X		
Vital Signs		X	X	X	X	X	X	X	X	X	X		
CBC		X	X	X	X	X	X	X	X	X	X		

Chemistry (CMP)		X	X	X	X	X	X	X	X	X	X			
Cholesterol/Lipid Panel		X		X	X	X	X	X	X	X	X			
PT/INR		X	X	X	X	X	X	X	X	X	X			
Serum Pregnancy Test (WOCBP Only)		X							X	X				
Urinalysis		X								X	X			
Tumor Assessments with RECIST 1.1 ⁵	X			←----- Every 8 weeks ⁵ ----- -----→									X ⁵	
ECHO/MUGA	X													
ECG (12 – Lead)		X ³		X	X	X	X ³	X	X	X	X			
Adverse Events ⁶	X	X		X	X	X		X	X	X	X			
Conmeds ⁶	X	X		X	X	X		X	X	X	X			
Biomarker Tissue Collection (Biopsy) ⁷	X ⁷					X ⁷								
Biomarker Blood Collection ⁸		X		X		X		X	X	X				
LEE011 Study Drug (Oral) ⁹				X		X		X	X					
Patient Dosing Diary for LEE011 ⁹				X		X		X	X					
Chemoembolization (TACE) ¹⁰				X		X		X	X					
Discontinuation ¹¹											X			
Survival Follow-Up ¹²													X	

1. Screening assessments, apart from those listed above, must occur within 28 days of registration as per Table 7.1;
2. Vital Signs, ECOG Performance Status, Physical Exam, ECG, CBC, CMP, PT/INR, Lipid Panel, Serum Pregnancy Test (WOCBP Only), and Urinalysis should be performed within 7 days of the first treatment day (Cycle 1, Day 1). If there are any dose modifications or halting of drug in the phase II aspect, weekly hematology, comprehensive metabolic panels, and PT/INR laboratory investigations will be performed until the grade of adverse event leading to the modification or cessation is stable or a grade reduction occurs. In addition, following each chemoembolization the following will be done every other week for two cycles after each chemoembolization: physical examination, CMP, CBC, and PT/INR.

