8. Biomarker blood collection is also an optional research procedure and the patient must have consented to the additional blood collection to participate (phase II only). Blood will be collected according to the schedule in table 7.1;
9. Patients will be treated with LEE011 (3 weeks on / 1 week off of a 28 day cycle) until disease progression, unacceptable toxicity, death, or discontinuation from the study treatment due to any other reason. The patient will complete a subject dosing log in order to ensure drug compliance. The patient will be provided a new dosing diary at each new treatment cycle and reviewed at the end of each cycle for compliance.
10. Patients will be treated with chemoembolization with up to 4 total chemoembolizations within the first 6 months from the initial chemoembolization.
11. Patients who discontinue treatment for reasons other than disease progression, death, start of new anti-neoplastic therapies, lost to follow-up, or withdrawal of consent to efficacy follow-up, then tumor assessments and patient reported outcomes must continue to be performed every 8 weeks during the first 12 months and every 12 weeks thereafter until the start of new anti-cancer therapy, disease progression, death, lost to follow-up, or withdrawn consent to efficacy follow-up;
12. All patients will be followed for survival status every 12 weeks regardless of treatment discontinuation until death, lost to follow-up, or withdrawal of consent to survival follow-up. Survival follow-up assessment may be made by a phone call to the patient or designated PHI, EPIC medical record review, or certified mail. At least 3 documented attempts should be made to contact the patient before the patient is considered lost to follow-up.
13. The follow-up visit after chemoembolization can be used as day 1 visit of each cycle if the decision is made to continue with LEE011 treatments.

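### The post-TACE fever rule in 6.12.6(c) has no exception for patients already exposed to LEE011, and no section orders a neutrophil count for fever

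*Combined protocol and SAP*

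**What the plan says.** Post-procedure care, item (c) of 6.12.6, reads: "Fevers <103 degrees F are normal during the first week following treatment and do not require cultures". Item (d) adds that "patients will be seen in the HCC multidisciplinary clinic 7-10 days following chemoembolization"; the blood count listed for that visit has no differential.

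Repeat procedures are covered in 6.12.7: "Repeat Chemoembolization (for either ipsilateral or contralateral disease) if indicated, should be performed at least 4 weeks apart", with up to four in the first 6 months. The entry condition is at most "Grade 2 hematologic toxicity with the exception of" creatinine and bilirubin limits. No separate aftercare is given there.

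Footnote 2 to Table 7.1 schedules further counts: "following each chemoembolization the following will be done every other week for two cycles after each chemoembolization: physical examination, CMP, CBC, and PT/INR". Footnote 13 says "The follow-up visit after chemoembolization can be used as day 1 visit of each cycle", if LEE011 is to continue.

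Febrile neutropenia is addressed elsewhere. Table 6.2 lists "Grade 3 or 4 febrile neutropenia" as a DLT. Table 6-4 defines grade 3 as ANC below 1.0 x 10^9/L with a single temperature above 38.3°C (101°F), or 38°C (100.4°F) or more for over one hour. The action is to interrupt LEE011 and restart one dose level lower; "If febrile neutropenia recurs, discontinue LEE011". Section 9.1 names it among the events suspected to be related to LEE011.

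**The concern.** The same temperature is handled in two ways. Between 101°F and 103°F for a single reading, or 100.4°F and 103°F if sustained, 6.12.6(c) calls the fever normal, while Table 6-4 treats it as meeting the febrile neutropenia temperature limit. Only an ANC taken at the time separates the two, and no section orders one because of fever.

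Two things are at stake. The first is safety: a neutropenic patient with liver disease could have a fever put down to embolization and not cultured. The second is toxicity classification. An event that is not recognized does not lead to the Table 6-4 dose reduction. In phase Ib cycle 1 it is also not counted as a DLT, and escalation there turns on one versus two DLTs among 3 to 6 patients (section 6.6).

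Neutropenia itself is foreseeable from the protocol's background. Grade 3/4 neutropenia occurred in 15 of 67 patients (22%) at LEE011 600 mg (Table 2-1), and at 43% with a different CDK4/6 inhibitor in 23 patients with HCC (section 1.6). Section 9.2 also lists infection and cholecystitis as expected after TACE, so fever in that week is not always benign.

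**Working it through.** The plan gives no figure to reproduce. The check is of timing: who is exposed, whether a count falls in the fever week, and whether that week lies in the DLT window.

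**Inputs**
- LEE011 starts at least 7 days after the first TACE (6.12.6). Start days s = 7 to 14 are used, matching the Table 7.1 post-TACE column; up to day 28 is allowed.
- Dosing is on days 1-21 of a 28-day cycle (6.3). Cycles are assumed not to be shifted by the repeat TACE.
- Repeat TACE is on day T after the first, T = 28 or later (6.12.7).
- Nominal counts are on C1D1, C1D15, C2D1, C2D15, C3D1 and C4D1 (Table 7.1), that is s, s+14, s+28, s+42, s+56 and s+84. Footnote 2 adds days 14, 28, 42 and 56 after the first TACE. The same footnote's first count after the repeat TACE is T+14, outside the week.
- Visit window: ±3 days (footnote 4).

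**Exposure.** In the week after the first TACE no LEE011 has been given, so there is no gap. Four procedures in 6 months less the first leaves at most 4 − 1 = 3 exposed fever weeks per patient in that period.

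**Entry condition.** At most grade 2 hematologic toxicity allows ANC down to 1.0 x 10^9/L, the edge of the febrile neutropenia range, and it is applied before the procedure only.

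**Counts with repeat TACE on day 28.** The last nominal count is on day 28 itself (footnote 2). The next is C2D1 on day s+28: day 35 for s = 7 and day 42 for s = 14. That is 7 to 14 days after the procedure, so days 1-6 hold no nominal count for any s from 7 to 14. The window can move one in by chance: for s = 7, C2D1 could be as early as day 35 − 3 = 32, which is day 4 after TACE.

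**Wider grid.** Start days 7-14 (8) by repeat TACE days 28-56 (29) give 8 x 29 = 232 timetables, unweighted and not a probability.

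| Feature | Timetables |
|---|---|
| No nominal count on days 1-6 after repeat TACE | 82 |
| At least one nominal count on days 1-6 | 150 |
| No nominal count even if days 0 and 7 are included | 42 |
| Whole fever week in cycle 1 | 36 |
| Any fever-week day in cycle 1 | 84 |
| No fever-week day in cycle 1 | 148 |

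**Counting by cycle day instead.** Using only the Table 7.1 cycle visits, a nominal count falls 1-6 days after TACE for 12 of 28 possible TACE days in cycles 1-2, and for 6 of 28 from cycle 3. If it must stay inside days 1-6 for every date the ±3 day window allows, both become 0 of 28.

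**DLT window.** Cycle 1 runs from day s to s+27, and the fever week from T to T+6. The whole week is in cycle 1 if T ≤ s+21: day 28 for s = 7, day 35 for s = 14. Some of it is in cycle 1 if T ≤ s+27: day 34 for s = 7, day 41 for s = 14.

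**Dosing in the fever week.** With T = 28, LEE011 dosing days in the week run from 0 (s = 7, rest week) to 7 (s = 14).

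**The case against.** The strongest objection is that 6.12.6 was written for the first TACE. It closes with the decision to initiate LEE011, and repeat procedures have their own section. If 6.12.6 does carry over, its restart conditions should too. LEE011 would then be withheld for at least 7 days, and hematologic toxicity would have to be grade 2 or lower before dosing. That stands as a possible reading. It would remove the missed interruption, because no dosing would fall in the fever week. It would not remove the missed DLT, the missed dose reduction or the missing culture, because the patient has already been exposed. If 6.12.6 does not apply to repeat TACE, those procedures have no written fever guidance, so the text needs clarifying either way.

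Second, the sentence concerns cultures only. It forbids neither cultures nor a count, the febrile neutropenia tables remain in force, and 6.7 leaves management to clinical judgment. Patients stay overnight, and phase Ib toxicity is reviewed as it occurs. All of this is correct and lowers the risk. But the tables act on an ANC that no fever rule orders, and toxicity review can only act on events that were recognized.

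Third, an ANC close to the procedure is likely, given the entry condition and the calendar counts, and most timetables in the grid (150 of 232) do have a count in days 1-6. That also stands. The claim is limited to counts not being triggered by fever and not being guaranteed in that week.

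**Conclusion.** The concern holds. After a repeat TACE, 6.12.6(c) as written lets a fever that meets the Table 6-4 temperature limit be handled as ordinary post-embolization fever without a current ANC. The existing safeguards narrow this gap but do not close it.

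Its size in events cannot be stated, because the documents give no febrile neutropenia rate; the risk is plausible but unquantified. A missed interruption requires LEE011 dosing in the fever week. A missed DLT requires a repeat TACE at or near the 4-week minimum in phase Ib.

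The conclusion rests on reading 6.12.6 as covering repeat TACE, which is inferred from footnote 13 and the lack of separate aftercare in 6.12.7. The timing figures also rest on nominal visit dates, LEE011 starts on days 7-14 and unshifted cycles. Confidence is medium. The change should be made because it is cheap and improves both safety and DLT ascertainment.

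**What to change.** Amend 6.12.6(c) so that the statement applies only to patients not yet exposed to LEE011, or with ANC of at least 1.0 x 10^9/L documented at the time of the fever.

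Add that, after a repeat TACE, any fever meeting the Table 6-4 threshold (a single reading above 101°F, or 100.4°F or more for over one hour) requires a same-day CBC with differential. If ANC is below 1.0 x 10^9/L, take cultures and apply Table 6-4, or Table 6.2 in phase Ib cycle 1.

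The cost is one or two sentences by amendment, a few extra blood counts, and occasional cultures for what proves to be ordinary post-embolization fever. Patients with an adequate ANC would still not need cultures.

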6.7 LEE011 DOSE MODIFICATION GUIDELINE- PHASE IB CYCLE 2+ AND PHASE II COMPONENTS

Management of severe or intolerable adverse reactions requires temporary dose reduction and/or interruption of LEE011 therapy. Refer to Table 6.3 for guidance. Dose increases once LEE011 has been reduced are not allowed.

Table 6.3 Dose Modification Guidelines

Dose Level	LEE011	
	Dose	Number of capsules & strength
Highest dose (0)	600 mg	3 x 200 mg capsules
First dose reduction (-1)	400 mg	2 x 200 mg capsules
Second dose reduction (-2)	200 mg	1 x 200 mg capsules
Third dose reduction (-3)	Discontinue Treatment of LEE011	

Recommendations for dose reduction, interruption, of discontinuation of LEE011 in the management of adverse reactions are summarized in Table 6-4, Table 6-5, Table 6-6, and Table 6-7. Clinical judgment and discretion of the treating physician should guide the management plan of each patient based on individual benefit and risk assessment.

**Table 6-4 LEE011 Dose Adjustment and Management Recommendations for
HEMATOLOGICAL ADVERSE REACTIONS**

THROMBOCYTOPENIA	
Toxicity/Grade	Dose Adjustment and Management Recommendations
Grade 1 ($\geq 75 \times 10^9/L$)	No dose adjustment required.
Grade 2 ($\geq 50 \times 10^9/L - <75 \times 10^9/L$)	No dose adjustment required.
Grade 3 ($\geq 25 \times 10^9/L - <50 \times 10^9/L$)	Dose interruption until recovery to grade ≤ 2 . Re-initiate LEE011 at the same dose level. If toxicity recurs at grade 3: discontinue LEE011
Grade 4 ($<25 \times 10^9/L$)	Discontinue LEE011.

Toxicity/Grade	Dose Adjustment and Management Recommendations
Absolute neutrophil count (ANC)	
Grade 1 ($\geq 1.5 \times 10^9/L$)	No dose adjustment required.
Grade 2 ($\geq 1.0 - < 1.5 \times 10^9/L$)	No dose adjustment required.
Grade 3 ($\geq 0.5 - < 1.0 \times 10^9/L$)	Dose interruption until recovery to $\geq 1.0 \times 10^9/L$. Re-initiate LEE011 at the same dose level. 
 If toxicity recurs at grade 3: temporary dose interruption until recovery to $\geq 1.0 \times 10^9/L$ and reduce LEE011 dose to the next lower dose level.
Grade 4 ($< 0.5 \times 10^9/L$)	Dose interruption until recovery to $\geq 1.0 \times 10^9/L$. Re-initiate LEE011 at the next lower dose level. 
 If toxicity recurs at grade 4: temporary dose interruption until recovery to $\geq 1.0 \times 10^9/L$ and reduce LEE011 at the next lower dose level.
Febrile Neutropenia	

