 - Physical examination
 - Comprehensive metabolic panel
 - Complete blood count without differential
 - Prothrombin time/INR

At this time the decision will be made to initiate LEE011 treatment.

LEE011 ADMINISTRATION WITH CHEMOEMBOLIZATION

Subjects are to be evaluated from toxicity with:

- Physical Examination (PE)
- Comprehensive Metabolic Panel (CMP)
- CBC
- ECG's

LEE011 will be initiated at the earliest of 7 days following embolization chemoembolization provided the following criteria are met:

- Serum bilirubin elevation $< 2.0 \times \text{ULN}$. If serum bilirubin $\geq 2.0 \times \text{ULN}$ then subjects will be assessed weekly and LEE011 will be initiated once bilirubin $< 2.0 \times \text{ULN}$.
- Resolution of Grade < 3 non-hematologic toxicity (other than bilirubin criteria above). If non-hematologic toxicity \geq Grade 3 then subjects will be assessed weekly and LEE011 will be initiated once $<$ Grade 2;
- Hematological toxicity of \leq Grade 2. If hematologic toxicity \geq Grade 3 then subjects will be assessed weekly and LEE011 will be initiated once \leq Grade 2.

If baseline AST, ALT and alkaline phosphate are elevated post chemoembolization decrease to baseline grade is necessary to continue/initiate LEE011;

- ECOG performance status ≤ 2 ;
- Serum AST, ALT, and/or Alkaline Phosphate $< 5 \times \text{ULN}$.

If criteria is not met, subjects will be reevaluated in 5-7 day intervals. If study subjects are unable to meet the above LEE011 starting criteria following initial chemoembolization treatment within 28 days after treatment, they will be removed from the study.

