10.3 LABORATORY ASSESSMENTS

Hematology, chemistry, coagulation, urinalysis, and cholesterol panels are to be performed according to the visit schedule outlined in Table 7.1 and 10.1.

Table: 10.1: Clinical Laboratory Parameters Collection Plan

Test Category	Test Name
Hematology	Hemoglobin, Platelets, white blood cells with differential (neutrophils, lymphocytes, basophils, eosinophils, monocytes)
Chemistry	Albumin, alkaline phosphatase, ALT, AST, creatinine, potassium, sodium, glucose, direct bilirubin,

	total bilirubin, total protein, magnesium, phosphorus
Cholesterol and Lipid Panel	Total cholesterol, LDL, HDL, triglycerides
Coagulation	PT, INR
Urinalysis	Glucose, protein, bilirubin, red blood cells, white blood cells, crystals, and bacteria.

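### Section 6.12.6 and Table 10.1 disagree on whether the blood count at the post-TACE visit that decides LEE011 start includes a differential, and the start criterion needs a neutrophil count

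*Combined protocol and SAP*

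**What the plan says.** Section 6.12.6, item d, states that "patients will be seen in the HCC multidisciplinary clinic 7-10 days following chemoembolization" and gives four evaluations for that visit. One is a "Complete blood count without differential". The list closes with "At this time the decision will be made to initiate LEE011 treatment".

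The next block, under the heading on LEE011 administration with chemoembolization, has its own list, introduced by "Subjects are to be evaluated from toxicity with". It names a CBC without saying whether a differential is included. The start criteria follow. One requires hematological toxicity no worse than grade 2. A patient at grade 3 or above is reassessed weekly until back to grade 2 or lower.

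Table 7.1 marks a CBC in the column for 7-14 days after chemoembolization and again at Cycle 1 Day 1. Footnote 13 adds that "The follow-up visit after chemoembolization can be used as day 1 visit of each cycle" if LEE011 is to continue.

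Section 10.3 says hematology follows the schedule in Tables 7.1 and 10.1. Table 10.1 defines the hematology panel as hemoglobin, platelets and "white blood cells with differential (neutrophils, lymphocytes, basophils, eosinophils, monocytes".

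**The concern.** The one place that spells out the type of count for the start-decision visit rules out the differential. The criterion applied at that visit covers hematological toxicity as a whole, and neutropenia is part of that. A count without differential yields hemoglobin, platelets and total white cells. It gives no ANC.

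Two things are at stake. The first is whether the existing start criterion can be applied in full. The second is attribution in phase Ib. Table 6.2 counts a first-cycle event as a DLT only if it is at least possibly related to LEE011. The procedure before LEE011 delivers doxorubicin-loaded beads. Without an ANC taken after TACE and before LEE011, a low count found later has no reference point between the two treatments. This trial has already had to separate them: Section 6.6 reports that cohort 1 was enlarged to 6 patients because of TACE-related toxicity that was not dose limiting.

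**Working it through.** No arithmetic applies. The check sets the relevant places side by side.

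| Place | What it covers | Differential |
|---|---|---|
| 6.12.6, item d | Count at the 7-10 day visit, where the start decision is made | Excluded |
| LEE011 administration list, after 6.12.6 | CBC for the toxicity evaluation | Not stated |
| Table 7.1, post-TACE column (7-14 days) | CBC | Not stated in the table |
| Table 7.1, Cycle 1 Day 1, with footnote 2 | CBC, within 7 days of Cycle 1 Day 1 | Not stated in the table |
| Section 10.3 and Table 10.1 | Hematology panel for the Table 7.1 visits | Required, neutrophils named |

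**Step 1: does the criterion need an ANC?** Table 6-4 grades neutropenia on ANC: grade 3 is 0.5 to below 1.0 x 10^9/L, and grade 4 is below 0.5 x 10^9/L. Deciding whether a patient is at grade 2 or lower therefore needs an ANC. The total white count bounds the ANC only from above, so a white count of 1.0 x 10^9/L or more does not exclude grade 3 neutropenia. Hemoglobin and platelets can be graded without a differential. Only the components that depend on the differential are affected.

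**Step 2: which readings leave an ANC gap?**
- *Tables 7.1 and 10.1 applied.* The post-TACE count includes neutrophils, and the criterion can be assessed.
- *6.12.6 list followed, separate Day 1 visit.* There is no ANC at the decision visit. Day 1 has its own CBC mark, which Table 10.1 defines with a differential, so an ANC is scheduled around the first dose.
- *6.12.6 list followed, and the visit used as Day 1 under footnote 13.* One draw serves both purposes. If it is the draw described in 6.12.6, there is no ANC between TACE and the first dose.

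**Step 3: does it reach the DLT assessment?** Under Table 6.2, neutropenia is a DLT when it is grade 4 for more than 7 consecutive days, or febrile at grade 3 or 4. Relatedness is a judgment, and a pre-dose ANC is direct evidence for it. Under Section 6.6, one DLT in 3 patients triggers expansion of cohort 2 or 3, and two in 3-6 patients move the dose down a level. A single attribution can therefore matter. The enrollment stopping rule in 6.6 counts events related to either LEE011 or TACE, so the split between the two does not affect it.

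**The case against.** The best defense is that the protocol, read as a whole, does specify an ANC. Section 6.12.6 presents its list as institutional routine. The list placed with the start criteria says only CBC. Section 10.3 links Table 7.1 to Table 10.1, and CBC is the only row of Table 7.1 that fits the hematology panel. A visit used as Day 1 also carries the Day 1 CBC, which Table 10.1 defines with a differential. This largely stands. A reader might infer from 6.12.6 that the neutrophil criterion cannot be checked anywhere in the protocol, and the documents do not support that. What remains is that 6.12.6 describes the same visit, states the opposite in explicit terms and ties it directly to the start decision. Nothing says which text prevails.

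Three further objections hold:
- At repeat TACE, footnote 2 adds a CBC every other week for two cycles after each procedure, and 6.12.7 sets a hematological condition before the next one. The gap should not be assumed to recur at every procedure.
- A low Day 15 ANC is not by itself a DLT, and an ambiguous event can still count as possibly related.
- Entry requires an ANC of at least 1,500 cells/mm3, and the expected TACE events in Section 9.2 do not list neutropenia.

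**Conclusion.** The contradiction is certain. Its practical effect is conditional. It needs a site that follows the 6.12.6 list rather than Table 10.1 and that merges the visits under footnote 13. On that path the neutrophil part of the start criterion cannot be assessed, and no ANC separates TACE from the first LEE011 dose.

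The size cannot be given as a number of patients. Every patient reaches this decision visit, but the documents do not say how sites would read the conflict or how often neutropenia follows TACE alone. A reader might use the grade 3/4 neutropenia rates of 22% (LEE011 600 mg, Table 2-1) or 43% (palbociclib in HCC, Section 1.6). Those were observed on drug and do not measure neutropenia after TACE and before LEE011. A reader might also infer that grade 3-4 neutropenia would go unseen for 14 dosing days, from Day 1 to the Day 15 count. That could happen only on the conditional path above, in a patient already neutropenic after TACE.

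The point still deserves correction because it concerns a safety check at treatment start and the evidence behind DLT attribution in small cohorts.

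**What to change.** Reconcile 6.12.6 with Tables 7.1 and 10.1 so that the count specified at the start-decision visit supplies the ANC on which the existing hematological criterion depends. Use the same description of the count in the list that precedes the start criteria, and make clear that it also applies when the visit serves as Day 1 under footnote 13. No threshold, dose or additional start condition is needed. In the same edit, reconcile the visit window, which is 7-10 days in 6.12.6 and 7-14 days in Table 7.1.

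The cost is a short wording amendment. The blood is already drawn at this visit, so the added laboratory cost is negligible.
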